3.3 EXPOSURE MEASUREMENT

Exposure will be defined as on-drug treatment or off-drug treatment. To identify exposure, all prescriptions for digoxin (or statins), dronedarone, and amiodarone will be identified and treatment episodes calculated. Statins of interest include atorvastatin, simvastatin, lovastatin, and pravastatin. Fluvastatin and rosuvastatin will not be considered for the potential interaction with dronedarone because they are not metabolized or only weakly metabolized by CYP3A4 and are not P-gp substrates.

Exposure will be categorized into the following three groups: 1) concomitant use of digoxin (or statins) and dronedarone, 2) concomitant use of digoxin (or statins) and amiodarone, and 3) digoxin (or statins) alone as the reference group, i.e. digoxin (or statins) without concomitant use of either dronedarone or amiodarone. The concomitant use of digoxin (or statins) and dronedarone (or amiodarone) will be defined as the treatment period during which a patient is on both of the drugs. Digoxin (or statins) alone will be defined as the treatment period during which a patient is on digoxin (or statins), but not on dronedarone or amiodarone. Amiodarone is included as part of exposure of interest because it is one of the major drugs that are identified to have potent interactions with digoxin (or statins) as a multi-channel blocker displaying antiarrhythmic properties of all four Vaughan-William's classes.

The treatment duration or follow-up time on digoxin (or statins) alone will begin accumulating on the first day of digoxin (or statins) prescription and continue with the subsequent continuous digoxin (or statins) prescriptions until: 1) a prescription for dronedarone (or amiodarone) overlapping the digoxin (or statins) days supplied, or 2) the end of the digoxin (or statins) days supplied (in addition to a grace period of up to 30 days, to account for non-adherence), 3) the occurrence of the outcome, 4) the enrollment end of membership, 5) the end of the observation period, whichever comes first. The follow-up time of the concomitant use of digoxin (or statins) and dronedarone (or amiodarone) will be defined using the same methodology as described above. It will however begin on the first day of overlapping days supplied for digoxin (or statins) and dronedarone (or amiodarone) and will finish with the end of overlap of the days supplied for digoxin (or statins) and dronedarone (or amiodarone) (in addition to a grace period of up to 30 days) or the other endpoints, whichever comes first. Prescriptions will be treated as continuous if they are not interrupted by a break of greater than 30 days. If a gap of greater than 30 days occurred, patients may still contribute follow-up time (defined as a separate treatment episode) to digoxin (or statins) alone or the concomitant medications as appropriate, until they are right-censored at the first occurrence of: 1) the outcome, 2) the enrollment end of membership, and 3) the end of the observation period.

Given that digoxin (or statins) may be administered at a lower dose when used in combination with dronedarone than the use of digoxin (or statins) alone, and the drug interaction effect may be dose-related, the average daily dose of digoxin (or statins) will be adjusted for as a covariate in the analysis. It will be calculated as the total quantity prescribed divided by the total days supplied. If a statistically significant association of interaction is observed, further analysis will be performed to check dose-response relationship. For statins, the analyses will be conducted at equally effective doses which will address the effect of dose with the same cholesterol lowering effect. Based on published literature comparing statins efficacy, the following equally effective doses will be used in the secondary analysis for statins: atorvastatin 10mg, simvastatin 20mg, lovastatin 40mg, and pravastatin 40mg¹⁻².

Both un-adjusted and adjusted odds ratios will be calculated using Cox proportional hazards regression modeling (see Section 3.7).

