3.5 COVARIATE(S)

The following covariates will be adjusted for in the multivariate analyses: age at baseline, gender, cohort entry date, duration of AF/AFL, congestive heart failure (CHF) history, diabetes history, hypertension history, stroke history, myocardial infarction history, and dose of digoxin (or statins). The major medications that are known to have potent interactions with statins or digoxin will additionally be adjusted for as potential confounders. For digitalis intoxication, the medications will be those with potent interactions, including arbutamine, atazanavir, calcium chloride, calcium gluceptate, calcium gluconate, and saquinavir. The drugs with interaction that are generally considered to be moderate (e.g. aspirin) or mild (e.g. acetaminophen) will not be considered⁷. For the outcome of rhabdomyolysis and myopathy, the major medications will include erythromycin, clarithromycin, azithromycin, fusidic acid, warfarin, dicoumarol, nefazodone, ketoconazole, itraconazole, cholestyramine, mibefradil, digoxin, gemfibrozil, cyclosporine, chlorzoxazone, and vitamins niacin⁸. History of renal failure (except for acute renal failure) will also be adjusted for the outcome of rhabdomyolysis and myopathy.

The history of the medical conditions will be defined as a diagnosis in the baseline period based on the ICD-9 codes (codes to be provided). The count of the number of diagnoses of AF/AFL in the baseline period will be used as a surrogate for the duration of AF/AFL since the accurate information is not available in the LabRx database. All medications will be identified using the National Drug Code (NDC) directory. Maintained by the Food and Drug Administration (FDA), NDC is a code-set that serves as a universal product identifier for human drugs and biologics. The directory consists of prescription and a few selected over-the-counter drugs that are in commercial distribution in the United States. The products have been listed in accordance with the Drug

Listing Act and applicable Code of Federal Regulations for submitting drug product information to the FDA (see: <http://www.fda.gov/cder/ndc/>).

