3.7 STATISTICAL ANALYSIS

Descriptive statistical analysis will be performed to characterize the study participants. Cox proportional hazards regression modeling will be used to provide estimates of the relative hazard of the outcome of interest associated with concomitant use of digoxin (statins) and dronedarone, and concomitant use of digoxin (statins) and amiodarone, using digoxin (statins) alone as the reference group. If a statistically significant association of interaction is observed, further analysis will be done to estimate dose-response relationship with cumulative dose and treatment duration.

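### The digoxin-alone reference pools time on other antiarrhythmics, and the only separate antiarrhythmic group is itself a potent interactor, so the dronedarone hazard ratio can mix interaction with treatment selection

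*Protocol*

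**What the plan says.** Section 3.3 sets three exposure groups: digoxin (or a statin) with dronedarone, with amiodarone, and alone. The third is "digoxin (or statins) alone as the reference group, i.e. digoxin (or statins) without concomitant use of either dronedarone or amiodarone", and section 3.7 fits the Cox model "using digoxin (statins) alone as the reference group". Exposure is built from a short list of drugs: "all prescriptions for digoxin (or statins), dronedarone, and amiodarone will be identified and treatment episodes calculated". The reason given for a separate amiodarone group is that "it is one of the major drugs that are identified to have potent interactions with digoxin (or statins".

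The groups are person-time, not separate sets of patients. Time on digoxin alone stops when dronedarone or amiodarone overlaps it, and a patient can contribute episodes to more than one group.

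Section 3.5 adjusts for "age at baseline, gender, cohort entry date, duration of AF/AFL, congestive heart failure (CHF) history, diabetes history, hypertension history, stroke history, myocardial infarction history", and for dose. Section 3.3 explains the dose adjustment: "Given that digoxin (or statins) may be administered at a lower dose when used in combination with dronedarone". For digitalis intoxication the co-medications adjusted for are potent interactors, "including arbutamine, atazanavir, calcium chloride, calcium gluceptate, calcium gluconate, and saquinavir". The same section adds: "All medications will be identified using the National Drug Code (NDC) directory".

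**The concern.** Dronedarone time is, by definition, time on an antiarrhythmic. Reference time is any digoxin time without two particular drugs. It mixes patients on no antiarrhythmic with patients on some other one, and the plan keeps no record of which is which. The only other antiarrhythmic group cannot show how often digitalis intoxication is recorded in patients chosen for antiarrhythmic treatment when no interaction is expected, because the protocol selected amiodarone for its interaction.

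If patients chosen for antiarrhythmic treatment differ in their risk of digitalis intoxication, or in how often it is recorded, and the covariates do not capture the difference, it enters the dronedarone hazard ratio. The protocol wants to rule out hazard ratios of 1.42 to 1.59 (section 3.6), so even a modest bias matters. It could hide an interaction or create the appearance of one, and the single planned contrast cannot tell these apart.

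**Working it through.** **Inputs from the protocol.** Two-sided alpha 0.05, power 80%, dronedarone prevalence 17.1%, baseline incidence 1.1%, right censoring 30%, 5-year digoxin cohort 44,000, hazard ratio to be ruled out 1.42 (section 3.6, Table 3), and an event trigger of 336 for a hazard ratio of 1.5 (section 5).

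**The plan's own figure.** Schoenfeld's formula gives events = (1.960 + 0.842)² / [0.171 × 0.829 × (ln 1.5)²] = 7.849 / (0.14176 × 0.16440) = 337, against 336 stated. The trigger is reproduced. For Table 3, 44,000 × 1.1% = 484 events, and the detectable hazard ratio is exp[2.802 / √(484 × 0.14176)] = 1.40, close to the stated 1.42. Removing 30% for censoring leaves 339 events and gives 1.50. No stated figure is disputed here.

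**Is antiarrhythmic choice captured?** Setting sections 3.3 and 3.5 side by side:
- Exposure uses digoxin or statin, dronedarone and amiodarone prescriptions only.
- The covariates hold CHF as a baseline diagnosis history and AF/AFL duration as a count of diagnoses. The protocol calls the latter a surrogate.
- The co-medication list is chosen by potent interaction with digoxin. An antiarrhythmic without such an interaction would not qualify for it, even if the list is read as open.

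Other antiarrhythmic use therefore enters neither the exposure nor the adjustment.

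**Possible bias (assumed values only).** For a factor with risk ratio R that remains unbalanced after adjustment, present in share p₁ of dronedarone time and p₀ of reference time, the bias factor is [1 + p₁(R − 1)] / [1 + p₀(R − 1)]. With R = 2 and a true hazard ratio of 1.42:

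| p₁ | p₀ | Bias factor | Apparent HR |
|---|---|---|---|
| 20% | 40% | 1.20/1.40 = 0.857 | 1.22 |
| 20% | 30% | 1.20/1.30 = 0.923 | 1.31 |
| 30% | 20% | 1.30/1.20 = 1.083 | 1.54 |
| 40% | 20% | 1.40/1.20 = 1.167 | 1.66 |

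A second illustration assumes no interaction, all dronedarone time carrying a selection effect g on recorded toxicity, and 10% of reference time carrying it too. The apparent hazard ratio is g / (0.9 + 0.1g), so g = 0.8, 1.25 and 1.5 give 0.82, 1.22 and 1.43.

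**Precision of a supplementary contrast (assumed shares).** Let s be the share of the 44,000 on digoxin with another antiarrhythmic. Events = 44,000 × (0.171 + s) × 0.011, a = 0.171 / (0.171 + s), and detectable HR = exp[2.802 / √(events × a(1 − a))].

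| s | Events | a | Detectable HR, no censoring | Detectable HR, 30% censoring |
|---|---|---|---|---|
| 5% | 107 | 0.774 | 1.91 | 2.17 |
| 10% | 131 | 0.631 | 1.66 | 1.83 |
| 20% | 180 | 0.461 | 1.52 | 1.65 |
| 30% | 228 | 0.363 | 1.47 | 1.59 |

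By the same method the planned reference gives 1.40 without censoring and 1.50 with it. Those two values treat everyone not on dronedarone as reference, with no share set aside for amiodarone, so they are slightly favourable.

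**The case against.** The objective is whether dronedarone raises digoxin's adverse events, and digoxin without dronedarone is a direct reference for that. The cohort is restricted to AF/AFL (section 3.2), a substantial covariate list is planned, and digoxin dose, the one group difference that the protocol names, is adjusted for. A dronedarone user's own digoxin-only time also counts as reference, so the groups are not disjoint. Amiodarone is measured against the same reference, so a clearly raised amiodarone estimate would suggest that the reference does not hide interactions generally. A supplementary contrast could also be left to a statistical analysis plan that is not shown here.

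Much of this stands. It supports keeping the planned reference and rules out calling a null result uninterpretable. It does not remove the point. The exposure groups are fixed in the protocol itself; the planned model is not a within-patient comparison, and the share of shared time is unknown; amiodarone patients may be selected differently, so that check is partial.

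A reader might infer more: that reference patients are mainly on rate control and have more severe heart failure, so that the bias must run towards false reassurance. The protocol says none of this. Nor does it say how many patients take digoxin with another antiarrhythmic, or which of those drugs leave digoxin levels unaffected. Identification by drug code shows that such time can be found, not that it is plentiful. The new group would also be selected by indication and need not be better balanced on severity.

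**Conclusion.** The point holds as a limit on interpretation, not as an error in a figure or a reason to discard the design. The digoxin-alone contrast can mix interaction with selection for antiarrhythmic treatment, and no other planned comparison separates the two. Neither the size nor the direction of any bias can be derived from the protocol. Under the assumptions above, a true 1.42 could appear anywhere from 1.22 to 1.66, and with no interaction the apparent value could lie between 0.82 and 1.43. These ranges presuppose that the imbalance remains after the planned adjustment, which may reduce it. The figures are for the digoxin cohort; the statin reference is defined in the same way, but its bias and precision are not quantified here.

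**What to change.** - Keep digoxin alone as the primary reference.
- In section 3.3, move digoxin time with another antiarrhythmic, and without dronedarone or amiodarone, into its own exposure category. The sponsor should pre-specify and justify the drug list and leave out drugs known to raise digoxin levels.
- Add the size of this group and its events to the annual counts in section 5.
- In section 3.7, pre-specify dronedarone against this group as a supplementary contrast, reported with its confidence interval.
- State that the digoxin-alone contrast cannot by itself separate interaction from treatment selection.

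The cost is one further exposure category and one further contrast from the same model, using prescription data already held. The main drawback is a wide interval if the group is small. For that reason a reassuring conclusion should not be made conditional on the two contrasts agreeing: it would rest the safety conclusion on a comparison of unknown and possibly low power.

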3.2 STUDY POPULATION

Separate study cohort will be identified according to the study objectives and the outcome of interest. To evaluate potential interaction of dronedarone and digoxin, patients aged 18 years and older with a diagnosis of AF/AFL (International Classification of Diseases, Ninth Revision, Clinical Modification (ICD-9) codes: 427.3X) who filled a prescription of digoxin since the launch of dronedarone in the US, will be identified from the LabRx[®] database. Likewise, to evaluate potential interaction of dronedarone and statins, we will identify patients aged 18 years and older with a diagnosis of AF/AFL who filled a prescription of statins since the launch of dronedarone. Cohort entry date will be defined as the date of the first prescription of digoxin (or statins) dispensed after July 21, 2009, the launch date of dronedarone in the US. The study observation period will be from July 21, 2009 to the latest date of available data by August 31 of each year in the yearly study report. Excluded from the cohort will be patients with the following conditions at cohort entry date: 1) less than six months of enrolment period in the managed care organization (UnitedHealthCare); 2) a diagnosis of the outcome of interest (prevalent cases) within the last six months.

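### Amiodarone co-use already running at cohort entry is pooled with new co-use, while nearly all dronedarone co-use is seen from its start, so the two hazard ratios should not be read side by side

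*Protocol*

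**What the plan says.** Section 3.2 fixes entry: "Cohort entry date will be defined as the date of the first prescription of digoxin (or statins) dispensed after July 21, 2009", which it gives as dronedarone's US launch date. Two exclusions apply at entry: "less than six months of enrolment period in the managed care organization (UnitedHealthCare"), and "a diagnosis of the outcome of interest (prevalent cases) within the last six months". Neither concerns earlier use of amiodarone, digoxin or a statin.

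Section 3.3 forms three exposure groups: co-use with dronedarone, co-use with amiodarone, and digoxin or statin alone as reference. Co-use with either drug "will be defined as the treatment period during which a patient is on both of the drugs". Of its follow-up time the section says: "It will however begin on the first day of overlapping days supplied for digoxin (or statins) and dronedarone (or amiodarone"). It does not say what happens when that first day lies before entry. A restart after a gap of more than 30 days counts as a further episode. Amiodarone is an exposure of interest because "it is one of the major drugs that are identified to have potent interactions with digoxin (or statins").

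Section 3.7 plans a hazard ratio for each co-use group against the reference and, after a significant association, a dose-response analysis by cumulative dose and duration of treatment.

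**The concern.** One rule serves both drugs, but their market histories differ. Dronedarone became available when the cohort opened, so its co-use starts under observation. The protocol treats amiodarone as an established interactor. A patient already taking it with digoxin or a statin enters the amiodarone group with the onset of co-use unseen.

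If the risk from an interaction changes with time since co-use began, or if susceptible patients have had the event or stopped co-use before entry, the two groups are measured at different stages. The six-month outcome exclusion can add to this. It can remove amiodarone co-users whose event came during earlier co-use. It can remove a dronedarone co-user only if the event fell between launch and that patient's own entry fill.

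The amiodarone hazard ratio is one of two planned for each outcome, and both share a reference group, so readers will probably set them next to each other. A known interactor with a distorted ratio could make the analysis look insensitive, or make two equal drugs look different.

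**Working it through.** **The protocol's own figure.** Section 5 gives 336 events to rule out a hazard ratio of 1.5. With two-sided alpha 0.05, 80% power and 17.1% dronedarone prevalence (Table 3), Schoenfeld's formula gives (1.960 + 0.842)² / [0.171 × 0.829 × (ln 1.5)²] = 7.849 / 0.0233 = 337. The figure reproduces. It concerns dronedarone only. The protocol states no amiodarone prevalence, no share of co-use already running at entry, and no hazard by time since co-use began.

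**Who can enter with co-use running.** A patient on continuous digoxin and amiodarone at launch enters at the next digoxin fill, soon after launch. Read literally, a patient who enters more than six months after launch has been enrolled for at least six months and has had no digoxin or statin fill since launch while enrolled. Co-use at that entry is new or restarted, even if amiodarone itself is long-standing. Ongoing co-use therefore comes mainly from early entrants.

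**Effect on the hazard ratio (assumptions only).** Let hE and hL be the early and late hazard ratios, e the share of new co-use time that is early, and f the share of amiodarone co-use time from episodes already running, all of it late. With a flat baseline hazard, the pooled ratio is approximately

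(1 − f)·e·hE + [1 − (1 − f)·e]·hL.

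With e = 0.5:

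| Shape (hE, hL) | f = 0 | 25% | 50% | 75% | 90% |
|---|---|---|---|---|---|
| Front-loaded (3, 1.2) | 2.10 | 1.88 | 1.65 | 1.43 | 1.29 |
| Constant (1.5, 1.5) | 1.50 | 1.50 | 1.50 | 1.50 | 1.50 |
| Rising (1.2, 2.0) | 1.60 | 1.70 | 1.80 | 1.90 | 1.96 |

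For example, front-loaded at f = 50%: 0.25 × 3 + 0.75 × 1.2 = 1.65. With e = 0.25 and f from 0 to 75%, the front-loaded row runs 1.65, 1.54, 1.43, 1.31 and the rising row 1.80, 1.85, 1.90, 1.95. The f = 0 column is what an identical drug observed wholly from onset would show.

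**Depletion of susceptible patients (assumptions only).** Under gamma frailty with variance θ, the ratio after T years of co-use is HR(1 + θH) / (1 + θ·HR·H). I take H = 0.011 × T, reading the protocol's 1.1% for digitalis intoxication as yearly, a unit it does not state. For a true ratio of 2:

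| θ | 1 year | 5 years |
|---|---|---|
| 0 | 2.00 | 2.00 |
| 1 | 1.98 | 1.90 |
| 5 | 1.90 | 1.65 |
| 10 | 1.82 | 1.48 |

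Depletion through the outcome alone is small unless susceptibility varies a great deal.

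**Duration and cumulative dose.** If overlap began d days before entry, a clock that starts at entry records t days of co-use where the true figure is d + t. Cumulative dose falls short in the same way. This needs no assumption about the hazard.

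**The case against.** A reader might infer that the amiodarone hazard ratio is understated and that dronedarone will look worse than an equal drug by a definite percentage. The documents do not support that. They say nothing on how the hazard moves with duration of co-use, and the bias vanishes or reverses under other shapes. Nor is 1.42 a bar for amiodarone: it is the detectable ratio for dronedarone with digoxin after five years of accrual, and the statin figure is 1.61.

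The problem is also narrower than it first looks. By Table 3, 44,000 − 25,000 = 19,000 digoxin patients (43%) and 86,000 − 58,000 = 28,000 statin patients (33%) accrue after year 3. Few of them can bring ongoing co-use. Not every dronedarone episode is new either: restarts count, and a few overlaps may begin between launch and the first later digoxin or statin fill.

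The objective concerns dronedarone. The protocol plans no contrast between the two antiarrhythmics and does not call amiodarone a benchmark. The reference group also contains long-standing digoxin or statin users, and an analysis plan that is not shown could add a split.

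Most of this stands, and it limits the point without removing it. The reference group has no onset of co-use to miss, so its own prevalent use does not cancel the imbalance. The exposure groups are fixed in Section 3.3, which mixes the two kinds of amiodarone co-use.

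**Conclusion.** The point holds in a limited form. As written, the plan pools ongoing and new amiodarone co-use, while nearly all dronedarone co-use is observed from its start. The amiodarone ratio may be understated (risk concentrated early, or susceptible patients depleted), unbiased (constant ratio without depletion) or overstated (ratio rising with duration). Its size cannot be derived from the protocol, and the tables above rest wholly on assumed inputs. Two consequences follow: the two hazard ratios should not be read side by side, and duration and cumulative dose are undercounted for ongoing amiodarone co-use. The dronedarone-versus-alone estimate is untouched, because amiodarone co-use lies outside the reference group. The change is worth making for the second planned estimate; the main objective does not depend on it.

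**What to change.** In Section 3.3, use the six months of enrolment before entry to classify amiodarone co-use:

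- **New:** no overlapping supply of amiodarone and digoxin (or statin) in the prior six months. The test is on overlap, not on amiodarone alone, so digoxin or a statin newly added to existing amiodarone still counts as new, as the same sequence does for dronedarone.
- **Already running at entry:** reported as its own exposure category.

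Neither category goes into the reference group. Apply the same definition of new co-use to dronedarone, and state how a restart within six months is classified, identically for both drugs. Base any side-by-side reading, and any duration or cumulative-dose analysis, on new co-use. If a numerical illustration accompanies the change, label it as assumption-only and show front-loaded, constant and rising hazards together.

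The cost is protocol wording, one more exposure category, and a wider interval for the amiodarone estimate because it rests on less person-time. No extra data are needed, since the look-back is already an entry condition. The planned dronedarone-versus-alone estimate and the 336-event trigger stay as they are.

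### As Section 3.3 reads, the main statin model adjusts for unconverted daily dose with no molecule term, so equal covariate values can differ up to four-fold in effective dose

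*Protocol*

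**What the plan says.** **Exposure class.** Protocol Section 3.3: "Statins of interest include atorvastatin, simvastatin, lovastatin, and pravastatin". These are treated as one class: "Exposure will be categorized into the following three groups: 1) concomitant use of digoxin (or statins) and dronedarone", then the same with amiodarone, then statins alone as reference. Section 3.7 plans one Cox contrast for the class.

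**Why dose is adjusted for.** Section 3.3: "Given that digoxin (or statins) may be administered at a lower dose when used in combination with dronedarone", and because the interaction may depend on dose, "the average daily dose of digoxin (or statins) will be adjusted for as a covariate in the analysis".

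**How dose is computed.** Section 3.3: "It will be calculated as the total quantity prescribed divided by the total days supplied". This one formula serves digoxin and statins alike and contains no conversion between molecules.

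**Where the equivalence enters.** After a sentence that makes dose-response work conditional on a significant association, Section 3.3 says that the statin analyses will be run at doses of equal cholesterol-lowering effect. The next sentence narrows this: "the following equally effective doses will be used in the secondary analysis for statins: atorvastatin 10mg, simvastatin 20mg, lovastatin 40mg", with pravastatin 40 mg as the fourth entry.

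**Covariates.** The Section 3.5 list ends with "stroke history, myocardial infarction history, and dose of digoxin (or statins"). It names neither statin molecule nor equivalent dose.

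**The concern.** The dose covariate has a stated job: to take out a difference in statin dose between concomitant time and statin-alone time, so that the dronedarone contrast is not distorted by it. Within one molecule, daily milligrams can do that. Across four molecules of different potency, the same number of milligrams stands for different amounts of drug effect. The protocol recognises this by listing equivalent doses, but appears to keep them out of the main model.

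A patient moved from atorvastatin 40 mg to pravastatin 40 mg keeps the same covariate value although, on the protocol's own scale, the effective dose has fallen to a quarter. If such differences were more common during dronedarone use, the pooled HR would absorb them. In a safety study, a shift toward less potent molecules could mask an interaction, and a shift the other way could mimic one.

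**Working it through.** **Inputs.** Equivalent doses from Section 3.3: atorvastatin 10 mg, simvastatin 20 mg, lovastatin 40 mg, pravastatin 40 mg. Section 3.3 gives no unit for quantity; I read it as milligrams, since a bare tablet count would not be a dose even within one molecule. The protocol states no figure of its own on this point to reproduce.

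**Range of effective dose at equal milligrams.** Effective units = daily mg / equivalent mg.

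| Daily mg | Atorvastatin | Simvastatin | Lovastatin | Pravastatin | Max/min |
|---|---|---|---|---|---|
| 10 | 1 | 0.5 | 0.25 | 0.25 | 4 |
| 20 | 2 | 1 | 0.5 | 0.5 | 4 |
| 40 | 4 | 2 | 1 | 1 | 4 |
| 80 | 8 | 4 | 2 | 2 | 4 |

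The pairwise ratios are 4 (atorvastatin to lovastatin or pravastatin), 2 (atorvastatin to simvastatin), 2 (simvastatin to lovastatin or pravastatin) and 1 (lovastatin to pravastatin). Four-fold is the largest gap, not the typical one.

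**Which analysis uses the conversion.** Three readings are open. (a) The unrestricted sentence governs all statin analyses, so the main model already converts. (b) The next sentence governs, so only the secondary analysis converts. (c) Both belong to the conditional dose-response work they follow, so conversion happens only after a significant result. The word secondary and the conversion-free formula favour (b) or (c). Under either, the main model carries unconverted dose.

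**Illustration of the consequence (every input here is an assumption).** Suppose no true interaction and a statin-alone mix of 40% atorvastatin, 40% simvastatin and 20% lovastatin or pravastatin. In concomitant time a share d moves from atorvastatin to lovastatin or pravastatin at unchanged mg. The hazard multiplies by r per doubling of effective dose, so relative hazards at equal mg are r², r and 1. Then

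apparent HR = [(0.4 − d)r² + 0.4r + (0.2 + d)] / [0.4r² + 0.4r + 0.2]

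- r = 1.2, d = 0.1: 1.212 / 1.256 = 0.965
- r = 1.5, d = 0.2: 1.45 / 1.70 = 0.853
- r = 2.0, d = 0.3: 1.7 / 2.6 = 0.654
- Opposite shift, r = 1.2, d = −0.1: 1.300 / 1.256 = 1.035
- Opposite shift, r = 2.0, d = −0.2: 3.2 / 2.6 = 1.231
- d = 0 or r = 1: exactly 1, no bias of this kind

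The sign depends on the direction of the shift and the size on r and d. The protocol supplies neither.

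**The case against.** The strongest reply is that the main-model reading is not settled. The unrestricted sentence can be taken as a statin-specific qualifier of the general formula, and Section 3.5 speaks only of dose, never of unconverted milligrams. That ambiguity is real. It does not clear the text, because the next sentence then assigns the equivalence to a secondary analysis. At the least, the two must be reconciled.

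A second reply is that an analysis plan could add a molecule term. It could, but the protocol already fixes both the formula and the covariate list, and the change proposed is to those choices.

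A third is that the equivalence measures cholesterol lowering, and nothing in the protocol shows that myopathy risk follows the same scale. That stands, and is a reason to add molecule as well as equivalent dose.

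Some stronger inferences are tempting but unsupported:

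- **That molecule choice does confound the contrast, or that the adjustment carries no information.** No molecule mix is given for either group, and unconverted dose remains informative within a molecule.
- **That pooling dilutes a true effect below what the study can detect.** This needs the share of use in sensitive statins and the baseline risk by molecule; the protocol has neither.
- **That the protocol implies different effects among the four retained statins, with pravastatin apart.** Section 3.3 says "Fluvastatin and rosuvastatin will not be considered for the potential interaction with dronedarone because they are not metabolized or only weakly metabolized by CYP3A4" and adds that they are not P-gp substrates. It ranks nothing among the four kept.
- **That the two excluded statins ought to serve as a negative control.** That is a design preference, not a correction.

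**Conclusion.** The point holds in limited form and should be corrected. Section 3.3 contradicts itself on whether the equivalence applies to the statin analyses generally or only to a secondary one. On the better-supported reading, the main-model covariate lets patients with the same value differ up to four-fold in effective dose, and no molecule term makes up for it. The four-fold figure is exact on the protocol's cholesterol-lowering scale and rests on reading quantity as milligrams. I hold the reading of the text with moderate confidence.

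The consequence is incomplete adjustment for a difference the protocol itself anticipates. Whether that biases the dronedarone HR, in which direction and by how much, cannot be determined from the document. It requires both a molecule mix that differs between concomitant and statin-alone time and a risk that depends on molecule or effective dose.

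**What to change.** - **Reconcile the two sentences in Section 3.3**, stating whether the equivalence applies to the primary statin model, and give the unit of quantity in the dose formula.
- **Primary statin model:** express dose as daily mg divided by the listed equivalent (10, 20, 40 or 40 mg). Add statin molecule to the Section 3.5 list, updated when a patient switches. Both are needed if dose enters linearly, because a single slope per mg would otherwise be shared by molecules of different potency. If dose enters on the log scale, the molecule terms absorb fixed potency ratios, but conversion keeps the coefficient readable.
- **Reporting:** give the dronedarone HR by molecule beside the pooled HR, labelled descriptive.

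Section 3.5 already identifies drugs by National Drug Code, so no new data are needed. The cost is wording, a few more model terms and wide molecule-level intervals.
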